13.3 Demographic Data and Baseline Comparability

Quantitative demographic data will be described by summary statistics (number of subjects, mean, standard deviation, median and range). The number and percentage of subjects will be presented for categorical variables. No formal statistical comparison

between the treatment groups will be performed. Demographic data summary will include age, gender and race. These data will be presented for the overall safety population only, unless the sample sizes for ITT and MITT subject populations are very different from that of safety population (differ by more than 3 subjects). In this case, demographic data will be presented for that population. Baseline efficacy assessments will also be presented by treatment group.

13.4 Data Adjustments and Derived Endpoints

13.4.1 Time Windows

Because some subjects may complete their assessments at times differing from the scheduled times, each such score will be adjusted so as to reflect more accurately the score that would have been observed had it been recorded at the scheduled time. With the exception of the 1-5 minute PPT evaluations, time windows will be created for each of the 5-minute scheduled PPT time points, the widths being ± 3 minutes. The time window for the 1-5 minute PPT evaluations will be ± 30 seconds.

- If an assessment is performed within a time point window, the corresponding value will be assigned to that time point (*e.g.*, an assessment performed anywhere between 3 and 7 minutes from the previous evaluation, regardless of when it was scheduled, will be assigned to the scheduled 5 minute time point).

If a particular time point has no value within its window, then the PPT or QST Heat value will be assigned using either Last Observation Carried Forward (LOCF) or Next Observation Carried Backward (NOCB). In particular, LOCF will be used for missing data prior to onset, and NOCB will be used for missing data after onset to conservatively estimate both onset and duration.

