Formulation	Sprays	Formulations	Sprays
CTY-5339-A	1	CTY-5339-CB	1
CTY-5339-A	2	CTY-5339-CB	1
CTY-5339-CB	1	CTY-5339-A	1
CTY-5339-CB	1	CTY-5339-A	2

To maintain double-blind conditions, the CTY-5339-CB subjects in the two spray sequences will also receive one spray with the vehicle control (CTY-5339-P). A third party not involved with evaluating subjects will administer the drug. The CTY-5339-P Vehicle will be sprayed outside the circumscribed area to avoid dilution of active drug. Efficacy evaluations will be done at 1-5 minute intervals beginning immediately after drug administration and will include:

Pin Prick (PPT) & QST Heat Sensation Tests:

For PPT, evaluations will be done at 1 minute intervals for the first 5 minutes to capture onset of anesthesia. Starting at 5 minutes after drug administration, both PPT and QST will be done at 5 minute intervals up to the one hour time point. If there is no indication of anesthesia by 10 minutes, the subject will be considered a treatment failure and the assessment of PPT and/or QST, as appropriate, will be discontinued. In addition, once onset of anesthesia has occurred, if there is no longer any anesthesia at two consecutive evaluation time points from 10 minutes onward, the assessment of PPT and/or QST, as appropriate, will be discontinued.

STUDY

Pin Prick Test (PPT): The PPT will be assessed, using a 90-mm, 26-

DESIGN: (cont) 1 gauge pencil-point spinal needle (Polymedic; Temena S.A., Bondy, France or equivalent). At screening, 3 pin pricks will be performed on each cheek. Pin pricks will be assessed using a 0 (no pain) to 10 (severe pain) Numerical Rating Scale (NRS). In order to be eligible for the study, for each cheek, subjects must have a minimum score of "3" for the last 2 pin pricks, and one of those scores has to be "4" or higher.

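### PPT windows of ±3 min on a 5-min grid overlap with no single-use rule, and the worked example contradicts them, so one off-schedule reading can count as two consecutive failures in the PPT co-primary duration endpoint

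*Combined protocol and SAP*

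**What the plan says.** Section 13.4.1 (Time Windows) contains four statements that bear on this point.

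- Width from 10 min on: "time windows will be created for each of the 5-minute scheduled PPT time points, the widths being ± 3 minutes". The sentence opens by excepting the PPT readings at 1 to 5 min.
- Width for the early readings: "The time window for the 1-5 minute PPT evaluations will be ± 30 seconds".
- Assignment: "If an assessment is performed within a time point window, the corresponding value will be assigned to that time point". Nothing says what happens when a reading lies in two windows or when two readings lie in one.
- Worked example, said to map to the 5-minute point whatever time the reading was due: "an assessment performed anywhere between 3 and 7 minutes from the previous evaluation".

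The section then fills points with an empty window, for PPT and QST alike: LOCF before onset and NOCB after it. The window widths are given for PPT only.

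Section 13.5 and the synopsis define duration as time from onset to treatment failure, with failure required at two consecutive time points. Section 9 sets the 5-min spacing.

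**The concern.** Requiring two consecutive failures protects the co-primary endpoint against one stray pin-prick response. That protection is lost if one reading may stand for two neighbouring points. A programmer following the text literally could end a subject's duration on one observation. Another, applying an unstated single-use rule, would get a different duration from the same data.

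The example adds two further conflicts. It implies another width, and it counts from the preceding evaluation, whereas the rule uses scheduled times. Both versions cannot be programmed.

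**Working it through.** **Inputs.** Half-width 3 min, ±30 s rule, assignment rule, example and NOCB: section 13.4.1. Spacing 5 min: section 9. Two-consecutive rule: section 13.5 and synopsis. QST timing: section 9. The timing SDs below are assumptions, because the documents give none.

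**1. The plan's own example.** A ±3 min window around 5 min is 5 − 3 = 2 to 5 + 3 = 8 min. The stated range is 3 to 7 min, which is 5 ± 2. It is not reproduced. It also differs from the window that actually applies to the 5-min PPT point, 5 ± 0.5 = 4.5 to 5.5 min.

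**2. Overlap from 10 min on.** Adjacent windows are t ± 3 and (t + 5) ± 3. The first ends at t + 3 and the next begins at t + 2, so they share 1 min. With 11 points from 10 to 60 min there are 10 adjacent pairs: 12-13, 17-18, and so on to 57-58. That is 10 of 50 min, or 20%. A reading 2-3 min early or late lies in two windows (at 10 and 60 min, on one side only).

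**3. Worked subject.** Anesthesia at 10 and 15 min; one failing reading at 22.4 min (a late 20-min reading); 25-min reading missed; anesthesia at 30, 35 and 40 min; failure at 45 and 50 min. Failure is dated at the first of the two points.

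| Rule | 20 min | 25 min | 30-40 min | 45, 50 min | Failure |
|---|---|---|---|---|---|
| Literal ±3 min | fail (17-23) | fail, same reading (22-28) | no fail | fail | 20 min |
| Each reading used once | fail | no fail, NOCB from 30 | no fail | fail | 45 min |

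The difference is 45 − 20 = 25 min. Dating failure at the second point gives 50 − 25 = 25 min as well.

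A reading at exactly 22.5 min gives 20 min under the literal rule too. With single use it gives 45 min if it is assigned to the 20-min point. If it is assigned to 25 min, the 20-min point is empty, NOCB fills it with the same failure, and the result stays at 20 min.

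**4. The opposite error.** A reading at 17.4 min shows anesthesia, the 20-min reading is missed, and 25 and 30 min fail. Literally, 17.4 min fills both 15 (12-18) and 20 (17-23), so failure is at 25 min. With single use, NOCB fills 20 from 25 and failure is at 20 min.

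**5. How often a reading lies in two windows.** For an interior point with normal timing error of SD s, the share is 2 × [Φ(3/s) − Φ(2/s)].

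- s = 0.5 min: about 0.01%
- s = 1.0 min: 2 × (0.99865 − 0.97725) = 4.3%
- s = 1.5 min: 2 × (0.97725 − 0.90879) = 13.7%

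Nine interior points plus half of each end point make 10 effective readings per session: 10 × 0.043 = 0.4 at SD 1.0 and 10 × 0.137 = 1.4 at SD 1.5.

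Some slippage is plausible. Heating from 35 to 51°C at 0.5°C/s takes 32 s, so three QST stimuli can take up to 3 × 32 + 2 × 30 = 156 s, after six pin pricks, in each 5-min cycle.

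**6. Anchor.** If each slot is counted 3 to 7 min from the one before, starting at 5 min, the 60-min slot could lie anywhere from 5 + 11 × 3 = 38 to 5 + 11 × 7 = 82 min. These are outer bounds that need eleven maximal deviations in one direction.

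**The case against.** **The example can be reconciled with the width.** With times in whole minutes and strict bounds, a ±3 window around 5 min holds 3, 4, 5, 6 and 7, and the later windows (8-12, 13-17, ...) no longer overlap. The plan states neither convention, however. Its ±30 s windows need finer times, and the anchor conflict would remain.

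**A false double failure needs more than an overlap.** The neighbouring point must have no reading of its own, or someone must make an unstated choice between two readings. If the worked subject has an on-time 25-min reading showing anesthesia and the nearest reading is used, failure is at 45 min. This stands, and it limits the size.

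**The width matters less than the missing tie-break.** A simulation assumed true failure from 45 min, a 10% chance of an isolated failing reading before that, timing SD 1 min and no missed readings. Failure dated before 40 min occurred in 5.9% of subjects under ±3 with the nearest reading used, 8.1% if any failing reading in the window counts, and 6.5% under ±2.5 with single use. So the fix removes the ambiguity and does not, in this setting, lower the rate below that of a sensible reading of the present rule. This stands.

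**Stronger readings that the documents do not support.**

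- A reader might infer that the 5-min PPT point falls under both widths and that a 2-8 min window takes in the minute-3 and minute-4 readings. The ±3 sentence expressly excepts the 1-5 min PPT readings, so the first PPT overlap is 12-13 min. Only the loosely worded example touches the 5-min point.
- A reader might infer that the example and the anchor also cause double use. A ±2 window alone gives no overlap, and the anchor is a separate fault that appears only in the example.
- A reader might take the synopsis rule for ending assessments, "if there is no longer any anesthesia at two consecutive evaluation time points from 10 minutes onward", as governed by these windows. It is a rule for conduct at the site. The endpoint rule is the one in section 13.5 and the synopsis efficacy definition.

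**Conclusion.** Wrong as written, and it should be corrected. The overlap and the conflict with the example follow from the text alone. The consequence applies directly to the PPT co-primary. For QST the fault is that no window is stated although empty windows are imputed.

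In an affected subject the shift can be large: 25 min on a 60-min scale in the worked case. How many subjects are affected cannot be determined from the documents. At assumed timing SDs of 0.5, 1.0 and 1.5 min, about 0.01%, 4% and 14% of interior readings lie in two windows, and only some of these would change a failure time. The error can shorten or lengthen duration, and nothing in the documents indicates that it favours one treatment. No sample-size or power figure depends on it.

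**What to change.** Amend section 13.4.1 before unblinding:

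- Define every window by time since dosing. Delete the 3-7 min example and its reference to the preceding evaluation.
- Keep ±30 s for PPT at 1-5 min.
- Use half-open, non-overlapping windows [t − 2.5, t + 2.5) for PPT from 10 min and for QST from 5 min.
- Use each reading for one time point only. If two readings fall in one window, use the one nearest the scheduled time.

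The half-open bound gives a boundary reading one home: 12.5 min belongs to 15, and 22.5 min to 25. Nearest-point assignment alone would not settle such a tie.

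Two limits remain. NOCB can still turn one failing reading into two when the preceding point is empty, as in the 22.5-min case above, so this should be acknowledged or handled separately. PPT readings between 5.5 and 7.5 min would have no window (5.5 to 7 min at present), and the text should say so.

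The cost is a change of wording; no additional data are needed.

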13.5 Statistical Methods for Efficacy Evaluations

The primary efficacy analyses will be based on Modified Intent-to-Treat Population. The key comparisons will include:

1. CTY-5339-A, one spray versus CTY-5339-CB, one spray

The co-primary efficacy variables are duration of effect as measured by PPT and QST Heat. Duration of effect is defined as the time (in minutes) from onset to treatment failure (*i.e.*, for PPT, an assessment of “Same/More” pain, and for QST, the average heat temperature is greater than the average heat temperature at Baseline (non-treated cheek), up to the 60-minute time point (at two consecutive time points). For those discontinuing from the study for any other reason, the time to treatment failure will be censored at the last assessment time.

The secondary efficacy variables include:

- Duration of effect (PPT and QST) for CTY-5339A two sprays versus CTY-5339-CB, one spray plus CTY-5339-P one spray

- Duration of effect (PPT and QST) for CTY-5339A two sprays versus CTY-5339-A one spray
- Onset of anesthesia in minutes for PPT and QST Heat
- Percentage of responders at each time point for PPT and QST Heat for both onset and duration

Continuous variables will be analyzed via an ANOVA model with treatment effects at each of assessed time points. Pairwise comparisons for variables related to percentages will be analyzed via chi square tests. The 95% confidence intervals of the treatment differences will be presented using normal approximation with continuity correction, if appropriate. Pairwise comparisons for time-to-event related variables will be analyzed via a log rank model with treatment effects. Median time to event will be estimated and the 95% confidence intervals for the median will be presented, if appropriate.

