3. CLINICAL PROTOCOL SYNOPSIS

TITLE: A double-blind, partial cross-over, incomplete factorial study to assess the local anesthetic efficacy and safety of CTY-5339 Anesthetic Spray (CTY-5339-A) when applied to the cheek mucosal tissue in normal volunteers

STUDY NUMBER: C-002

PRINCIPAL INVESTIGATOR: [name], Director Clinical Pharmacology Research Unit, Dept. of Oral and Maxillofacial Surgery/Pharmacology, University of Pennsylvania, School of Dental Medicine

SITE: University of Pennsylvania, School of Dental Medicine
[name].

STUDY OBJECTIVES: This study is designed to assess the efficacy and safety of locally applied CTY-5339 Anesthetic Spray compared to 14.0% benzocaine alone in normal volunteers using experimental sensation including pinprick with a needle (PPT) and heat sensation threshold (QST). The objective of this study is to demonstrate that the combination of the two constituents in the CTY-5339 Anesthetic Spray (CTY-5339-A) provides longer acting local anesthesia than 14.0% benzocaine alone (CTY-5339-CB). The primary objective is to demonstrate that the CTY-5339-A one-spray dose is superior to CTY-5339-CB. The secondary objective is to demonstrate that the CTY-5339-A up to two sprays is a safe dosage.

HYPOTHESIS: CTY-5339-A when locally applied to cheek mucosal tissue in the mouth will have an onset comparable to the fastest constituent, benzocaine, and a prolonged effect comparable to the longest acting constituent, tetracaine, of the combination product. The study also is designed to demonstrate that both the CTY-5339-A one- and two-spray dosages are safe. (The assumption being made is that benzocaine has a faster onset of action than tetracaine.)

**STUDY
DESIGN:**

This is a single-dose, partial cross-over, double-blind and single-center study with an active control treatment. All subjects will remain at the study center for each of the two 60 minute test sessions. The subjects will be tested at two different test sessions separated by 4-14 days.

The study will include 76 subjects who will be evaluated for 60 minutes at each test session. At each session, a circular area of approximately one inch in diameter will be isolated on one side of the inner cheek using an indelible oral pencil. Each session will use a different side of the cheek. The possible sequences of treatments with the metered spray at the two sessions are:

Session 1		Session 2	

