During each treatment session, at Baseline and at each post-dosing time point, 3 pin pricks will be performed first on the non-treated cheek and then on the treated cheek. At Baseline, pin pricks on both cheeks will be assessed using a 0 (no pain) to 10 (severe pain) NRS. Post-Baseline, pin pricks on the non-treated cheek will also be assessed using the 0 to 10 NRS, but on the treated cheek, the three repetitions will be compared to the non-treated cheek as "No pain", "Less Pain" or "Similar/More Pain". For each cheek, the first pin prick will not be used for analysis. Of the remaining 2 pin pricks, the one with the most severe pain rating will be used for analysis. During each treatment session, in order for a subject to be eligible to continue in the study, for each cheek, both of the last 2 Baseline assessment pin pricks must have a minimum score of "3" for the last 2 pin pricks, and one of those scores has to be "4" or higher. Post-Baseline, an assessment of "No Pain" or "Less Pain" at a drug application site will be recorded as presence of analgesia/anesthesia ("Responder").

Heat sensation threshold (QST-Heat): The heat stimuli are delivered in 3 repetitions, with inter-stimulus intervals of 30s. The basal thermode temperature is set at a comfortable 35°C. The rate at which the thermode heats up is set at 0.5°C/s, while the rate at which it cools down is set at 8°C/s. The maximum thermode temperature is set at 51°C. (Note: Hot beverages such as tea and coffee are frequently served at temperatures between 50°C - 60°C. Burns can occur at 65°C.²⁵). Heat sensation threshold will be defined as the temperature at which the subjects first feel tingling, warmth, heat, or pain.

At screening, QST-Heat assessments will be performed on each cheek. In order to be eligible for the study, for each cheek, subjects must have a mean Heat sensation threshold of 48.5°C or less, based on the last 2 of the 3 readings.

During each treatment session, for each assessment, the first stimulus will be disregarded and the remaining two stimuli will be averaged for data analysis (unless the first two readings are 51°C, in which case the third assessment will not be done). At Baseline and at each post treatment assessment, the heat sensation threshold will be performed on the treated cheek only. During each treatment session, in order for a subject to be eligible to continue in the study, subjects must have a

**STUDY
DESIGN: (cont)**

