mean Heat sensation threshold of 48.5°C or less, based on the last 2 of the 3 readings. Post-Baseline, the presence of analgesia/anesthesia will be defined when the heat sensation threshold at the treated site is higher than the Baseline (“Responder”).

All tests on the treated cheek will be done near the center of the circumscribed area, but in a slightly different place at each consecutive evaluation time point. All tests on the non-treated cheek will be performed at approximately the same part of the cheek as those on treated cheek.

Randomization: A randomization code will determine the sequence of treatments and to which circumscribed area the treatment is administered (left or right cheek). Sensory testing will be done in the following order: pin prick followed, where applicable, immediately by heat sensation tolerance.

Subjects retain the right to withdraw from the study at any time.

EFFICACY MEASUREMENTS

The primary comparison of interest is one spray of CTY-5339-A compared to one spray of CTY-5339-CB. Co-primary efficacy variables are duration of effect as determined by PPT and duration of effect as measured by QST Heat. Duration of effect is defined as the time (in minutes) from onset to treatment failure (for PPT, treatment failure occurs when an assessment of “Same/More” pain, and for QST, a treatment failure occurs when the average heat temperature is the same or less than the average heat temperature at Baseline up to the 60-minute time point (at two consecutive time points).

The secondary efficacy variables include:

- Duration of anesthesia (PPT and QST Heat) for the two sprays of CTY-5339-A compared to one spray of CTY-5339-CB plus CTY-5339-P
- Duration of anesthesia (PPT and QST Heat) for the two sprays of CTY-5339-A compared to one spray of CTY-5339-A
- Onset of anesthesia for PPT and QST Heat
- Percentage of responders for PPT and QST Heat for both onset and duration
- Percentage of responders for PPT and QST Heat at each time point

OTHER MEASUREMENTS

At Baseline and at the end of the 60-minute test session an ECG, vital signs, and a 7 mL blood draw will be taken. The blood will be analyzed for the occurrence of subclinical methemoglobinemia by the HUP – Pepper Lab via co-oximetry analysis. At screening and throughout each test session, subjects will also be monitored with pulse oximetry. Methemoglobinemia is being defined as >5% of a subject’s

hemoglobin in the methemoglobin state, or a pulse oximetry reading of less than 91%.

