APPENDIX 2: CRITERIA FOR A “RESPONDER”

PPT:

Based on “No Pain” or “Less Pain” response to the pain stimulus at each observation time when compared to the non-treated site, subjects will be classified as “Responders” or “Non Responders”. At each observation, 3 pin pricks will be performed at each site (first on the non-treated cheek and then on the treated cheek). The first pin prick will not be used for analysis. Of the remaining two pin pricks, the one with the most severe pain rating will be used for the data analysis. If the most severe pain rating at that time point is “No Pain” or “Less Pain”, then the subject at that time point is a “Responder”.

QST:

The actual temperature data will be recorded at each time point. Temperatures will be recorded for "first sensation of tingling, warmth, heat, or pain". Scores will be censored at 51°C, if no response is obtained. If the average heat sensation temperature at each time point is greater than the average heat sensation temperature at Baseline, then the subject at that time period will be considered a “Responder”.

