QST: The heat stimuli are delivered in 3 repetitions, with inter-stimulus intervals of 30s. The basal thermode temperature is set at a comfortable 35°C. The rate at which the thermode heats up is set at 0.5°C/s, while the rate at which it cools down is set at 8°C/s. The maximum thermode temperature is set at 51°C. The first stimulus is disregarded and the remaining two stimuli are averaged for data analysis. In situations where a maximal analgesia/anesthesia effect is demonstrated in the initial two repetitions, the QST test will not be repeated for the third repetition and the data will be recorded as maximal effect (51°C) based on the first two repetitions.

Heat sensation threshold will be defined as the temperature at which the subjects first start to feel tingling, warmth, heat, or pain. All tests will be done near the center of the circumscribed area, but in a different place at each evaluation time point. For QST, the first time point after Baseline will begin at 5 minutes after drug administration. Subjects will have a hand held mouse that turns off the heat probe when they first start to feel tingling, warmth, heat, or pain. At the maximum heat level of 51° C, the heat probe turns off automatically. With a brief exposure at 51° C, there is no damage to the mucosal tissue.²⁵

Randomization: A randomization code will determine in which circumscribed area each treatment is administered (left or right cheek). Immediately prior to beginning each 60 minute test session, both the contra-lateral cheek and the cheek to be dosed will be evaluated with the PPT. For QST, the screening assessments will be performed on both cheeks, while during each treatment Session, at Baseline and all post-dosing time points, assessments will be performed on the treated cheek only.

Subjects retain the right to withdraw from the study at any time.

The PPT and QST tests will be done near the center of each evaluation area but in a different place at each evaluation time point. For PPT, the non-treated control cheek will always be tested before the treated area. The testing will be done in the following order where applicable: PPT and then QST.

A safety phone follow-up call will occur 3 days (± 1 day) after the Session 1 and 15 days (± 2 days) following Session 2.

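### Section 13.5 ends QST duration when the threshold is above Baseline, which is the response condition, and takes Baseline from a cheek with no QST reading that session

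*Combined protocol and SAP*

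**What the plan says.** **Failure, Section 13.5.** Duration of effect runs from onset to treatment failure. For QST, failure is the condition "the average heat temperature is greater than the average heat temperature at Baseline (non-treated cheek", required at two consecutive time points up to 60 minutes.

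**Failure, synopsis (Efficacy Measurements).** The same endpoint has the opposite rule: "a treatment failure occurs when the average heat temperature is the same or less than the average heat temperature at Baseline".

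**Response.** The synopsis says "the presence of analgesia/anesthesia will be defined when the heat sensation threshold at the treated site is higher than the Baseline". Appendix 2 classes a subject as a responder on this condition: "If the average heat sensation temperature at each time point is greater than the average heat sensation temperature at Baseline". The synopsis Statistical Analysis section repeats it.

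**Cheek tested.** The synopsis states that at Baseline and after treatment "the heat sensation threshold will be performed on the treated cheek only". Section 9 agrees: "at Baseline and all post-dosing time points, assessments will be performed on the treated cheek only". So do the flow chart in Section 4, Appendix 1B and Section 11.2.2. QST is done on both cheeks only at screening. The synopsis adds: "Each session will use a different side of the cheek".

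**Role of the endpoint.** Section 13.5 makes QST duration co-primary with pin-prick (PPT) duration. Section 13.6 declares success if either is significant.

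**The concern.** Section 13.5 has two faults in one clause. The inequality points the wrong way, so a subject fails while the anesthetic is working. The reference cheek is also one that receives no QST at that session's Baseline.

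The clause defines one of two endpoints, either of which can carry the study. An analyst who follows it must either stop for lack of data or choose a substitute Baseline that the plan does not name. Choosing the treated-cheek Baseline while keeping the inequality produces a number that no longer measures duration.

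Sessions that never show an effect are a separate matter. The synopsis already deals with them: "If there is no indication of anesthesia by 10 minutes, the subject will be considered a treatment failure".

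**Working it through.** The plan gives no numerical result, effect size or standard deviation for this endpoint, so there is no figure of its own to reproduce. The check compares the texts and then applies both rules to the visit schedule.

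**1. Direction.** Let T be the mean of the retained readings at a visit and B the Baseline.

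| Source | Condition | Meaning given |
|---|---|---|
| Synopsis, Appendix 2 | T > B | response |
| Synopsis, Efficacy Measurements | T ≤ B | failure |
| Section 13.5 | T > B | failure |

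The PPT half of the Section 13.5 sentence describes loss of effect (pain similar to or worse than the untreated side). The QST half therefore cannot be read as describing continued effect.

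**2. Reference cheek.** In Session 1 the non-treated cheek has a screening value, and a Baseline that will be taken only at Session 2, 4 to 14 days later. In Session 2 it has the screening value and the Session 1 Baseline, 4 to 14 days old. Neither belongs to the same session, and no text authorizes using either.

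**3. Sessions affected.** The synopsis gives 38 exposures to each regimen of the combination and 76 to benzocaine alone: 38 + 38 + 76 = 152, matching its total. The primary comparison uses 38 + 38 = 76 sessions, or 38 + 76 = 114 if all benzocaine sessions were pooled. None has a same-session QST Baseline on the non-treated cheek.

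**4. Effect of the inequality alone.** Assumptions: the treated-cheek Baseline is substituted; QST visits are at 5, 10, ..., 60 minutes; onset is the first visit with T > B, here 5 minutes; the effect is continuous through visit L, then T ≤ B. Taking L = 10, 15, ..., 60 gives 11 profiles.

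*Synopsis rule.* The failing visits are L + 5 and L + 10, which needs L + 10 ≤ 60, so L ≤ 50. Dated at the first, duration is (L + 5) − 5 = L. Dated at the second, it is (L + 10) − 5 = L + 5. For L = 55 or 60 it is censored at 60 − 5 = 55.

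*Section 13.5 direction.* T > B already holds at 5 and 10 minutes in every profile. Duration is 5 − 5 = 0 (first) or 10 − 5 = 5 (second).

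| Last visit with effect, L (min) | Synopsis rule: first / second point | Section 13.5 direction: first / second point |
|---|---|---|
| 10 | 10 / 15 | 0 / 5 |
| 15 | 15 / 20 | 0 / 5 |
| 30 | 30 / 35 | 0 / 5 |
| 50 | 50 / 55 | 0 / 5 |
| 55 or 60 | censored at 55 | 0 / 5 |

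Starting the search at the visit after onset does not rescue the rule. Every profile with L ≥ 15 then gets 5 minutes (first) or 10 (second), and L = 10 never fails.

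If every session in both arms has the same event time, the number of events equals the number at risk. The log-rank observed-minus-expected and its variance are then both 0.

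**5. Effect at the 5-minute visit only.** Under the synopsis rule, failing visits at 10 and 15 give 5 minutes (first) or 10 (second). Under the Section 13.5 direction, T > B never occurs twice in a row, so the session is censored: at 15 − 5 = 10 minutes if testing stops after two visits without anesthesia, or at 55 if it continues. Either exceeds the 0 or 5 minutes given to a sustained effect.

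**6. Size of that mis-ranking, for an assumed mix.** Suppose 15 of 38 benzocaine sessions have this brief profile and all other sessions are sustained. There is one event time, with 76 at risk and 38 + 23 = 61 events. The combination has 38 observed events against 61 × 38/76 = 30.5 expected. The variance is 61 × 0.5 × 0.5 × (76 − 61)/75 = 3.05, so |z| = 7.5/√3.05 ≈ 4.3, in favor of the shorter-acting treatment. The 15 is an assumption, used only to show the direction of the error.

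**The case against.** The best defense is that this is a drafting slip whose intent can be recovered. The synopsis states the failure rule coherently. Section 8.4 describes duration as time to the first non-responder event, and the testing rule in the synopsis and Section 9 stops assessment after two visits without anesthesia. All point to loss of effect, and a programmer would probably notice the reversal. This stands as evidence of intent. It does not correct Section 13.5, which is the statistical methods text, and the plan states no order of precedence. Reversing the inequality would also leave the wrong cheek in place.

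A second objection is that identical durations, and hence a log-rank test with no information, arise only if every session shows a sustained effect. That is right: brief effects would be handled differently, as step 5 shows. The rule can then favor the shorter effect, which is worse than being uninformative.

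Third, Sections 10.3 and 13.5 list benzocaine plus vehicle as its own regimen, so 76 is the more natural session count and 114 applies only under pooling. Neither figure measures bias.

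Fourth, the dating of failure is minor. With a common onset it moves uncensored durations and medians by 5 minutes but leaves their order, and so the log-rank result, unchanged. The synopsis sentence about differences between treated and non-treated sites does not name QST and fits PPT. Both points are tidying, and the main finding does not rest on them.

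**Conclusion.** The concern holds and must be fixed before the blind is broken. The QST failure rule in Section 13.5 is the protocol's own response condition, contradicts the synopsis, and refers to a Baseline not measured in the session. The error lies in Section 13.5, not in every statement of the endpoint.

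The reversal and the missing reference follow from the text alone. The durations in the table rest on the stated assumptions: a substituted treated-cheek Baseline, onset at 5 minutes and a continuous effect. On those terms, profiles that should run from 10 minutes to 55 (censored) all collapse to 0 or 5, and an effect seen only at 5 minutes is ranked as lasting longer than any of them.

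**What to change.** In Section 13.5, define QST treatment failure as a mean threshold at or below that session's treated-cheek Baseline at two consecutive visits, in line with the synopsis and Appendix 2. Delete the parenthetical reference to the non-treated cheek.

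While the text is open, make two smaller edits. State whether the first or the second of the two visits dates the failure, since the synopsis does not say. In the synopsis Statistical Analysis section, limit the sentence on treated versus non-treated site differences to PPT.

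The cost is a few words in Section 13.5, one sentence in the synopsis, and one dating decision recorded before unblinding. Data collection is unchanged.
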